Thank you for completing the Explant Forms and returning the device. Medtronic uses this information to meet FDA requirements and track product performance.

EXPLANT PROCEDURE OBSERVATION FORM

PATIENT INFORMATION	
Patient IDE/ Study ID	
Name:	
DOB (Month/Day/Year):/	
IMPLANT INFORMATION	
Date of Implant:/	
Implanting Physician:	
Implanting Hospital Name:	
City and State:	
Country:	
EXPLANT INFORMATION Date of Explant/Autopsy://	
Explanting Dhysician:	
Explanting Physician:	
Name of Hospital:	
Address:	
City and State:	
Country:	
Telephone: ()	
REASON FOR EXPLANT	
REASON FOR EAFLANT	
☐ Planned Surgical Conversion	
☐ Emergent Conversion	
☐ Autopsy Date of Death:/	
Remarks about procedure:	

Medtronic

Evidence of inflammation	\square Yes \square No	
Comments: Thrombosis present in the sealzones		
Comments:Calcification present in the sealzones		
Comments:		
How well was the device attached to the p	patient's tissue?	
Proximally : □ Comes out easily from ao	ortic vessel	
☐ Appears firmly attached t	o aortic vessel	
Mid body: ☐ Comes out easily from an	neurysm contents	
☐ Appears firmly attached t	o aneurysm contents	
Distally (L) : □ Comes out easily from ili	ac/aortic vessel	
☐ Appears firmly attached t	o iliac/aortic vessel	
Distally (R) : □ Comes out easily from ili	ac/aortic vessel	
☐ Appears firmly attached t	o iliac/aortic vessel	
Comments		
Successful Surgical Conversion: Yes		

EXPLANTED DEVICE INFORMATION

DEVICE	CATALOG NUMBER	LOT NUMBER
Bifurcated Body		
□ Distal Left		
□ Distal Right		
Contralateral Limb		
Iliac Extension		
□ Left		
□ Right		
Iliac Extension		
□ Left		
☐ Right Iliac Extension		
□ Right		
Aortic Cuff		
7 tortio our		
AUI		
□ Distal Left		
□ Distal Right		
Thoracic, Proximal Main		
Thoracic, Distal Main		
Thoracic, Distal Main		
Thoracic, Proximal Extension		
Thoracic, Distal Extension		
Other (Specify)		
	Additional Comments	
		_
Form completed by:		
Title:		
Date:		

L.5 Informed Consent Template

L.6 Post PMA-S approval Analysis

Following PMA-S approval, the postmarket evaluation will be conducted and results provided to the FDA once the last subject in the study completes the 12-month follow-up visit.

A synopsis of this post-approval proposal along with statistical assumptions is presented in Table L-1 below. Medtronic has used its experience with Valiant Captivia in patients with DTAA to establish the assumptions used in the statistical design of this study. The VALOR II study with the Valiant stent graft system enrolled 160 patients with DTAA and was assessed through 12 months for purposes of PMA (P100040) approval. Through 1-year post-treatment, the rate of MDEs combined with access and/or deployment failures was 7.1% (11/153) (Medtronic internal data using the Valiant Evo proposed definition). Therefore, for the purpose of post approval analysis, the rate of MDEs combined with access and deployment failures at 1-year with Valiant Evo is estimated to be 7.1% (refer to Table L-1 below for power analysis assumptions).

Table L-1: Power Analysis Assumptions for Evaluation of Valiant Evo in Patients with DTAA at 1-year

Estimated rate of MDEs combined with access and/or deployment failures at 1 year with Valiant Evo	7.1%
Performance Goal (PG) at 1-year	20%
Significance level	0.05
Statistical test	One-sided binomial test
Evaluable sample size	N = 63 at 1 year
Enrollment	IDE cohort will enroll a minimum of 100 subjects and is expected to have a minimum of 63 evaluable subjects at 1-year follow up.
Statistical power from 63 or more evaluable subjects	92% (overall study power for passing both hypotheses is 81%)

L.7 CMS Study Criteria

Medicare beneficiaries may be affected by the device because in 2013 more than 63% of TEVAR cases were performed in Medicare beneficiaries, and 59% of claims with principal TAA diagnoses involve patients age 65 or older. Study results are expected to be generalizable within the Medicare beneficiary population based on the prevalence of TAA in patients age 65 and older.

All IRBs should comply with 45 CFR part 46.

M VERSION HISTORY

Version	Summary of Changes	Author(s)/Title
1A	Not Applicable, New Document	
1B	 Synopsis update with schedule of events for extended follow-up Extended the follow of subjects from 12 months to 60 months Administrative changes like correction of typo's, font types and alignments, integration of updated corporate template

7. 7. 7. 7. 7. 7. 7. 7. 7. 7.	3. Data Pooling 4. Handling of Missing Data and Dropouts	.9 .9 10 10 10 10 11 11 16 17
7. 7. 7. 7. 7. 7. 7. 7. 8.	3. Data Pooling	

Version History 1.

Version	Summary of Changes	Author(s)/Title
1.0	New document	
2.0	Update SAP according to the CIP amendment - increasing subject follow-up requirements through period to 60 months (5 years). The analyses of corresponding outcomes are all extended to 5 years.	

2. List of Abbreviations and Definitions of Terms

Abbreviation	Definition
AE	Adverse Event
CEC	Clinical Event Committee
CIP	Clinical Investigation Plan
CRF	Case Report Form
DMC	Data Monitoring Committee
DTAA	Descending Thoracic Aortic Aneurysm
DMC	Data Monitoring Committee
IDE	Investigational Device Exemption
IPR	Independent Physician Reviewer
FDA	The US Food and Drug Administration
MAE	Major Adverse Event

Valiant Evo US Clinical Trial Statistical Analysis Plan

Version 2.0 Nov 1, 2017

This document is electronically controlled. Printed copies are considered uncontrolled.

MDE	Major Device Effect
MedDRA	Medical Dictionary for Regulatory Activities
OUS	Outside the United States
PG	Performance Goal
РМА	Premarket Approval
PMA-s	Premarket Approval - Supplement
PT	Preferred Term
SAE	Serious Adverse Event
SAS	Statistical Analysis System
SOC	System Organ Class
US	The United States

3. Introduction

This document outlines the detailed statistical methods to be implemented for the data collected within the scope of Valiant Evo US Clinical Trial and in conjunction with data collected during the concurrently enrolling Valiant Evo International Clinical Trial. This document is designed for internal use as a guideline for study Biostatistician and Statistical Programmer(s). Study protocol of the Valiant Evo US Clinical Trial is the primary resource if clarification is needed for the contents of this document. Analysis results obtained from the analyses outlined in this document will be the basis of the Clinical Study Report for this study.

As with any statistical analysis plan, the proposed methods and approaches to the data analysis should be viewed as flexible. Changes to the plan may arise if the emerging picture suggests that deviations from the original plan would provide a more reliable and valid analysis of the data. The purpose of this plan is to provide general, and in some instances, specific guidelines from which the analysis will proceed. Nonetheless, sound statistical reasoning must substantiate deviations from these guidelines.

4. Study Objectives

The purpose of the Valiant Evo US Clinical Trial is to demonstrate the safety and effectiveness of the Valiant

Valiant Evo US Clinical Trial Statistical Analysis Plan Version 2.0 Nov 1, 2017

This document is electronically controlled. Printed copies are considered uncontrolled.

Evo Thoracic Stent Graft System in subjects with a descending thoracic aortic aneurysm (DTAA) who are candidates for endovascular repair.

The clinical evidence collected as part of this trial will be used in conjunction with data collected during the concurrently enrolling Valiant Evo International Clinical Trial to support PMA Approval of the Valiant Evo Thoracic Stent Graft System.

5. Investigation Plan

The Valiant Evo US Clinical Trial is a prospective, multi-center, pre-market, non-randomized, single-arm trial.

Subject population will include subjects diagnosed with DTAA who are considered candidates for endovascular repair, and who meet the Inclusion/Exclusion Criteria for the Valiant Evo US Clinical Trial. Inclusion and exclusion criteria are defined in the Clinical Investigation Plan Section D.

At enrollment, those subjects who sign and date the informed consent document, meet all of the study eligibility criteria, and are approved by the IPR will be eligible for inclusion into the Valiant Evo US Clinical Trial. The subject will only be considered enrolled when arterial access is established and an attempt to introduce the Valiant Evo Thoracic Stent Graft is made. A single, primary stent graft may be used by itself if its size is sufficient to provide the desired coverage. Alternatively, it may be used in combination with additional stent graft sections that increases the graft length distally or proximally to the primary section.

The Valiant Evo Global Clinical program will be conducted under both the Valiant Evo US Clinical Trial protocol and Valiant Evo International Clinical Trial protocol, and will enroll up to 37 sites worldwide. Inclusion will be halted at sites that reach the 20% inclusion cap. There will be no minimum number of subjects for a single investigational site. Globally, a total of 100 subjects will be concurrently enrolled in the United States and outside the United States to support the primary endpoints. Up to 50% of subject data used to support PMA approval may come from subjects enrolled at sites outside of the US under the Valiant Evo International Clinical Trial protocol.

The primary endpoint analysis will be completed upon 87 evaluable subjects reaching the 30 day endpoint. The data obtained from these 87 evaluable subjects will be used to support PMA-s Approval of the Valiant Evo Thoracic Stent Graft System and to support any other future Medtronic submissions to regulatory bodies.

Subjects enrolled under the Valiant Evo US Clinical Trial require follow-up evaluations at the following time points:

- 1 month following the index procedure (30 ± 15 days)
- 6 months following the index procedure (183 ± 30 days)
- 12 months following the index procedure (365 ±60 days)
- 24 months following the index procedure (730 ±60 days)
- 36 months following the index procedure (1095 ±60 days)

Valiant Evo US Clinical Trial Statistical Analysis Plan Version 2.0 Nov 1, 2017

This document is electronically controlled. Printed copies are considered uncontrolled.

- 48 months following the index procedure (1460 ±60 days)
- 60 months following the index procedure (1825 ±60 days)

Note that the 6-month follow up is not mandatory for subjects enrolled under the Valiant Evo International Clinical Trial protocol. Available 6-month follow-up data from the international trial will be used for analysis.

Subjects will be followed until the last subject enrolled has completed the 1 year follow-up visit or until PMA approval is obtained in the US (whatever is later), however, Medtronic will work with FDA to determine if longer term follow after PMA approval is required. A post-approval analysis of 1-year Major Device Event (MDE) rate is planned.

6. Determination of Sample Size

One hundred (100) enrolled subjects will ensure 87 evaluable subjects at 30 days. The primary endpoint analysis will be completed upon 87 evaluable subjects reaching the 30 day endpoint. Based on Valor II study results, Valiant Evo is expected to perform similarly and have 6% of MDE combined with access and/or deployment failures at 30 days. The sample size of 87 evaluable subjects will provide 85% statistical power for the study hypothesis. The type I error is controlled at the one-sided 0.025 level.

True rate of MDEs combined with access and/or deployment failures at 30 day with Valiant Evo	6%
Performance Goal	16%
Significance level	0.025
Statistical test	One-sided binomial test
Evaluable sample size	n=87
Enrollment	Minimum of 100 subjects enrolled to ensure 87 evaluable subjects
Statistical power from the 87 evaluable subjects	85%

Table 1: Power Analysis

One hundred (100) enrolled subjects will also ensure 63 evaluable subjects at 1-year on MDE rate for the post-approval analysis. The VALOR II study with the Valiant stent graft system enrolled 160 patients with DTAA and was assessed through 12 months for purposes of PMA (P100040) approval. Through 1-year post-

Valiant Evo US Clinical Trial Statistical Analysis Plan Version 2.0 Nov 1, 2017

This document is electronically controlled. Printed copies are considered uncontrolled.

treatment, the rate of MDEs combined with access and/or deployment failures was 7.1% (11/153) (Medtronic internal data using the Valiant Evo proposed definition). Therefore, for the purpose of post approval analysis, the rate of MDEs combined with access and deployment failures at 1-year with Valiant Evo is estimated to be 7.1% (refer to Table 22 below for power analysis assumptions).

Estimated rate of MDEs combined with access and/or deployment failures at 1 year with Valiant Evo	7.1%
Performance Goal (PG) at 1-year	20%
Significance level	0.05
Statistical test	One-sided binomial test
Evaluable sample size	N = 63 at 1 year
Enrollment	IDE cohort will enroll a minimum of 100 subjects and is expected to have a minimum of 63 evaluable subjects at 1-year follow up.
Statistical power from 63 or more evaluable subjects	92% (overall study power for passing both hypotheses is 81%)

Table 2: Power	r Analysis for	Post-approval	Analysis of 1-	year Endpoint
----------------	----------------	----------------------	----------------	---------------

7. Statistical Methods

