7.9. Evaluation of Objectives

Primary Endpoint

The primary objective will be assessed by the composite safety and effectiveness endpoint that is based on the proportion of subjects who experienced:

- (a) Access and/or deployment failures; and/or
- (b) Major device effects (MDE) within 30 days post index procedure

MDEs include the occurrence of any of the following:

- Device-related secondary procedures
- Device-related mortality
- Conversion to open surgery
- Thoracic aortic aneurysm rupture

Detailed definitions of MDEs are defined in Clinical Investigational Plan Appendix L.5.

The primary study endpoint will be tested against a performance goal of 16% at 30 days:

 $H_0: p \ge 16\%$ vs. $H_a: p < 16\%$,

where p denotes the true event rate of primary study endpoint in the target population. If the null hypothesis

Valiant Evo US Clinical Trial Statistical Analysis Plan Version 2.0 Nov 1, 2017

This document is electronically controlled. Printed copies are considered uncontrolled.

(H₀) is rejected at the one-sided 0.025 statistical significance level, it is considered that the performance goal for the primary endpoint has been reached.

The analysis set of all enrolled subjects will be used for the analysis. The primary study endpoint is a dichotomous study outcome; hence, an exact method based on the binomial distribution will be used for the hypothesis testing.

Primary Endpoint Calculation:

A subject will be a failure on the primary endpoint if the subject either failed on access/deployment or had an MDE within 30 days. A subject will be a success on the primary endpoint if the subject is confirmed for access and deployment success as well as free from MDE. The failure rate of the primary endpoint is the percent of failures in all the evaluable subjects for the endpoint, i.e., in total number of failures and successes. Note that a subject who had an MDE within 30 days is one of the subjects in m as defined below. A subject who is free from MDE is one of the subjects in k as defined below.

MDE Rate Calculation:

All MDEs will be adjudicated by the Clinical Event Committee (CEC) per study protocol. MDE rate will be calculated as follows (Table 5):

MDE rate = m/(m + k)	Within 30 Days	Within 183 Days	Within 365 Days

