m = No. of Subjects Who Had MDE(s)	No. of subjects who had at least one MDE with onset day from Day 0 to Day 30, inclusive.	No. of subjects who had at least one MDE with onset day from Day 0 to Day 183, inclusive.	No. of subjects who had at least one MDE with onset day from Day 0 to Day 365, inclusive.
k = No. of Subjects Who Had No MDE	No. of subjects who have been in study for at least 1 day and without an MDE.	No. of subjects who have been in study for at least 91 days and without an MDE.	No. of subjects who have been in study for at least 305 days and without an MDE.

Table 5: MDE Rate Calculation:

If a subject is early terminated from the study, the last day that the subject has been seen will be the duration in study, which can be the day of last follow-up, last imaging taken, an AE reported, or withdrawal from the study. If a subject is still in the study, the duration in study will be the time from index procedure to the cut off day that the database is locked or data snapshot is taken.

Subgroup analyses by-sex, by-race (based on subjects enrolled in the US only, since collection of race and ethnicity data may not be allowed outside the US as per local law and regulation), FreeFlo versus Closed Web configuration as proximal component, percutaneous access versus non-percutaneous, and by-region/study site will be performed on the primary study endpoint using descriptive statistics and reviewed for

Valiant Evo US Clinical Trial Statistical Analysis Plan

Version 2.0 Nov 1, 2017

This document is electronically controlled. Printed copies are considered uncontrolled.

clinical significant difference.

Secondary Endpoints

30-day Secondary Endpoint

The following secondary endpoints will be evaluated within 30 days post treatment:

- Peri-operative mortality
- All adverse events (AE) within 30 days including:
 - Major Adverse Event(s) (MAE)
 - Serious Adverse Event(s) (SAE)
- Secondary procedures
- Loss of stent graft patency at 30 day visit based on imaging findings
- Endoleaks at 30 day visit based on imaging findings

Detailed definitions of MAEs are defined in the Clinical Investigational Plan Appendix L.2.2. MAEs will be identified using codes in the Medical Dictionary for Regulatory Activities (MedDRA) provided by the Medtronic Clinical Safety group.

6-month Secondary Endpoints:

The following secondary endpoints will be evaluated:

- All-cause mortality within 183 days
- Aneurysm-Related Mortality within 183 days
- MDEs within 183 days

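### Does the 1-year post-approval test lack a defined endpoint because the SAP sometimes calls it the MDE rate and writes the composite counting rule for 30 days only?

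*SAP*

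**What the plan says.** Two places in the SAP use the short name. Section 5 says "A post-approval analysis of 1-year Major Device Event (MDE) rate is planned", and section 6 says "One hundred (100) enrolled subjects will also ensure 63 evaluable subjects at 1-year on MDE rate for the post-approval analysis".

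The same section 6 then gives the quantity in full: "for the purpose of post approval analysis, the rate of MDEs combined with access and deployment failures at 1-year". The first row of Table 2 reads "Estimated rate of MDEs combined with access and/or deployment failures at 1 year with Valiant Evo", with 7.1% assumed, a 20% goal, one-sided 0.05, a binomial test, 63 evaluable subjects and 92% power. Protocol L.6 carries the same table. Protocol C.3 says that the primary endpoint is tested against 20% at 1 year, and C.1.2 points to L.6 for the 12-month hypothesis.

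For counting, SAP 7.9 has two pieces:

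- The composite rule: "A subject will be a failure on the primary endpoint if the subject either failed on access/deployment or had an MDE within 30 days". Success requires confirmed access and deployment success and freedom from MDE. The rule then says that subjects with a 30-day MDE are among Table 5's m, and MDE-free subjects are among its k.
- Table 5, with columns for 30, 183 and 365 days. At 365 days, m is subjects with an MDE from Day 0 to Day 365, and k is "No. of subjects who have been in study for at least 305 days and without an MDE".

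SAP section 3 says which document prevails: "Study protocol of the Valiant Evo US Clinical Trial is the primary resource if clarification is needed for the contents of this document".

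**The concern.** A programmer told to produce the 1-year MDE rate will find a Table 5 column that fits that name. It counts MDEs only, and SAP 7.9 contains neither a 1-year hypothesis nor a 365-day composite sentence.

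Used alone for the test, that column would mishandle subjects who fail access or deployment without an MDE:

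- Protocol F.1 and F.2.2 follow non-implanted subjects for 1 month. Such a subject is in neither m nor k at 365 days, so a composite failure disappears.
- F.2.2 keeps serious adverse event recording open for treatment failures, and SAP 7.9 bases an early-terminated subject's duration on the last day seen, "which can be the day of last follow-up, last imaging taken, an AE reported, or withdrawal from the study". A report at Day 305 or later could place that subject in k as event-free.
- An implanted deployment failure with at least 305 days in study also goes into k.

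Each route helps the device or leaves the result unchanged. At stake is a narrower endpoint tested against a goal set for the wider one. Only the post-approval test is exposed; the 30-day primary test has its own written rule.

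**Working it through.** **1. The plan's own figure.** Inputs from SAP Table 2: n = 63, goal 0.20, one-sided alpha 0.05, assumed rate 0.071. The exact test passes at the largest c with P(X ≤ c | 63, 0.20) ≤ 0.05.

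- P(X ≤ 7) = 0.047 and P(X ≤ 8) = 0.094, so c = 7.
- Power = P(X ≤ 7 | 63, 0.071) = 0.923, against the stated 92%.

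The 7.1% is the VALOR II composite rate, given as 11/153, so the stated power is already that of the composite test.

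**2. Which endpoint.** Protocol C.3 (primary endpoint against 20%), Protocol L.6, SAP Table 2 and the sentence of SAP 6 introducing that table all name the composite. SAP 5 and one sentence of SAP 6 use the short name. The Protocol synopsis and C.5 use the same shorthand at 30 days, calling the 16% goal an MDE rate although the endpoint is the composite. With the protocol as the primary resource, the composite is the only reading that fits all the passages.

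**3. Which counting rule.** Put the 365-day m and k into the composite rule of SAP 7.9:

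| Subject | Composite rule with the 365-day column | Table 5 alone |
|---|---|---|
| MDE by Day 365 | failure | in m |
| Access or deployment failure, no MDE, not implanted | failure | in neither; in k if a late report sets duration at 305 days or more |
| Deployment failure, implanted, no MDE, ≥ 305 days | failure | in k |
| Access and deployment success, no MDE, ≥ 305 days | success | in k |

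The middle rows come out correctly in the second column because access or deployment failure has no follow-up condition in the rule, and success requires confirmed access and deployment.

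**4. Size under the unsupported reading (Table 5 alone).**

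- At n = 63, 8 failures do not pass. If one is counted event-free, 7/63 passes (p = 0.047). If one is deleted, 7/62 does not pass (p = 0.053). If two are deleted, 6/61 passes (p = 0.027).
- Since 63 is a minimum, take n = 63 to 100 and a result one failure above the limit. One deletion reverses it wherever the limit at n − 1 equals the limit at n: 31 of 38 values, the exceptions being 63, 69, 76, 82, 88, 94 and 100.

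The documents give no rate for access or deployment failure without an MDE, so a = 1%, 2% and 3% is assumed. The MDE rate among the other subjects is q = (p − a)/(1 − a), where p is the true composite rate. The number deleted is Bin(n, a), and the test uses the limit for the remaining n.

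| n = 63, deletion | a = 1% | a = 2% | a = 3% |
|---|---|---|---|
| Chance of passing, p = 20% (composite test: 4.7%) | 5.1% | 6.1% | 8.0% |
| Composite fails but deletion passes, p = 7.1% | 1.7% | 4.4% | 6.4% |

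Over n = 63 to 100 with p = 20%, the chance of passing by deletion is 3.9–6.0%, 6.0–8.5% and 8.0–11.9% for the three values of a.

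**The case for a change.** The strongest case for a change is that deferring to the protocol settles which endpoint is meant but not how to count it: Protocol C.3 and L.6 give no numerator or denominator. The SAP is written for programmers and calls its own methods flexible. A hypothesis test should have its rule written in advance, and a sentence would cost nothing in sample size, goal, alpha or power.

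Part of this stands. SAP 7.9 has no 365-day composite sentence, and the short name in sections 5 and 6 is loose. What does not stand is the step to harm. Reaching Table 5 alone means setting aside Protocol C.3 and L.6, SAP Table 2 and the composite rule printed directly above Table 5. That rule links itself to m and k, and Table 5 supplies the 365-day versions. The requested sentence would only write down the rule that follows.

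**Conclusion.** No change follows. The 1-year endpoint is the composite, and its counting rule is the 30-day rule with Table 5's 365-day column supplying the MDE part. An analyst following both documents reaches it, with every access or deployment failure counted whatever the later follow-up. The label is a clerical looseness and the missing sentence is ordinary detail. Table 5's MDE-only column has its own use, the descriptive 12-month endpoint of MDEs within 365 days.

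The planned n = 63, the 20% goal, one-sided 0.05 and 92% power are consistent with the composite. The figures for distortion (for example 5.1% to 8.0% against 4.7% at n = 63) depend on two things the documents do not supply: use of Table 5 alone, and an assumed 1% to 3% rate of access or deployment failure without an MDE. They also set the true rate at the 20% goal. At the planned 7.1% and n = 63, the chance of a changed conclusion would be about 1.7% to 6.4% under that same reading.
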